3.7.1. Exposure

The time on study will be defined as the total number of days a subject is known to be followed on study calculated as follows:

$$\text{Time on study} = \text{Last date on study} - \text{Date of first dose} + 1,$$

where the last date on study is defined as the date of the latest visit with evaluation for a given subject. Visits with refused or unable to contact are not visits with evaluation

3.7.2. Adverse Events

The incidence of adverse events (AEs) will be summarized by Medical Dictionary for Regulatory Activities (MedDRA) Version 22.0 (or higher) preferred term (PT) and system organ class (SOC) for:

- Any treatment emergent adverse events (TEAEs).
- Related TEAEs. Related is defined as “Related”, “Possible”, or missing relationship to Study Drug.
- Any TEAEs by severity. At each severity level of subject summarization, a subject is classified according to the highest severity if the subject reported one or more events. AEs with missing severity will be categorized as “Missing” for this summary.
- Serious TEAEs.
- TEAEs leading to permanent Study Drug discontinued.

Serious and non-serious AEs that lead to study discontinuation or investigational drug discontinuation will be listed separately. Non-TEAE will be included and be noted in the subject AE listing.

To determine the AE as treatment-emergent or not, if there is no “Formlink” link, and the AE (start date/time) occurs after the subject’s first dosing date/time, then the AE is treatment-emergent. Otherwise, if the AE (start date/time) occurs prior to the subject’s first dosing date/time, then the AE is not treatment-emergent.

In addition, if there is a “Formlink” link between two AE records, then we compare them pairwise, and consider two cases, where we compare the AE severity (mild/moderate/severe) and seriousness (Yes/No) between the two records in the pair. We chronologically order the 2 records (by AE start date) and refer to the “first” and “second” AE.

Case 1: The first AE record in the pair occurs before first dosing, and the second AE record occurs after first dosing.

If the AE severity or seriousness of the second record is worse than that of the first record, then only the second AE is deemed as a TEAE. Otherwise, neither record is considered as TEAE.

Case 2: Both AE records in the pair occur after first dosing.

Only the worst AE will be deemed as one TEAE.

All TEAEs identified based on the rules above will be summarized in the event number analysis.

Missing Date for Adverse Events

For AEs, the following imputation rules will be applied to impute missing date under conservative principles.

Missing or partial start dates:

If year, month and day are all missing then assign the date of first administration of Study Drug

- If month and day are missing and year is:
 - the same as the year of the first administration of Study Drug then assign the month-day of first Study Drug
 - earlier than the year of the first administration of Study Drug then assign December 31
 - after the year of the first administration of Study Drug then assign January 1
- If only day is missing and month-year is:
 - the same as the month-year of the first administration of Study Drug then assign the day of first Study Drug
 - earlier than the month-year of the first administration of Study Drug then assign the last day of the month
 - after the month-year of the first administration of Study Drug then assign the first day of the month

Imputation will be performed for the end date only if the day or month is missing (i.e., year is present) for a stop date as follows:

- If month and day are missing and year is
 - the same as the year of the last dose of Study Drug then assign the month-day of the last dose of Study Drug
 - otherwise, assign December 31
- If only day is missing then assign the last day of the month

If the imputed start date is later than the imputed end date then set the imputed start date to the imputed end date.

Local Cutaneous Reactions at the Injection Site

Local cutaneous reaction at injection site (LCRIS) is defined as (A) moderate or severe adverse events with the PTs Injection site erythema, Injection site swelling, Injection site pruritus, or Injection site pain that started on the day of injection, persisted for at least two days or ongoing; or (B) any AE at the Study Drug injection site, regardless of severity, that leads to discontinuation of Study Drug, where AE at the Study Drug injection site is the principal reason for discontinuation.

Percentage of injections leading to LCRIS will be calculated as follows for each subject:
(A/B)*100, where A = number of injections with an LCRIS, and B = total number of injections. Doses that are split across multiple injections are counted as a single injection.

LCRIS will be summarized using the MedDRA coding system, by SOC/PT. Percentage of the injections leading to LCRIS at injection site will also be summarized.

LCRIS will be listed by preferred term.

Flu-like Reactions

Flu-like reactions are defined as adverse events with PTs including either (A) Influenza like illness or (B) Pyrexia or Feeling hot or Body temperature increased, plus at least two of the following symptoms with the PTs: Chills, Myalgia, or Arthralgia, starting on day of injection or the next day.

Percentage of injections leading to flu-like reactions will be summarized using the descriptive statistics.

Percentage of injections leading to flu-like reactions will be calculated as follows for each subject: $(A/B) * 100$, where A = number of injections leading to flu-like reactions, and B = total number of injections.

FLRs will be summarized using the MedDRA coding system, by SOC/PT. Percentage of the injections leading to FLRs at injection site will also be summarized.

FLRs will be listed by preferred term.

AE of Special Interest (AESI)

Per protocol, severe reductions in platelet count $< 50,000/\text{mm}^3$ accompanied by a clinically relevant bleeding event or platelet count of $< 25,000/\text{mm}^3$ independent of a clinically relevant bleeding event are considered as AESI. The AEs meeting the AESI criteria will be captured in the AE CRF page with a check box to indicate.

AESI will be summarized using the MedDRA coding system, by SOC/PT. A listing of AESI will also be generated.

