9.4.2. Non-Serious Adverse Events

The recording of non-serious AEs will begin after the patient signs the ICF and will stop at the end of the patient's Follow-up Period, which is defined as PTWk15/ETPT visit, or the last visit when patient withdraws consent. The Investigator will monitor each patient closely and record all observed or volunteered AEs on the Adverse Event Case Report Form.

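### AE end dates known only to the year of the last dose are set to the last-dose date, which can misdate a few AEs and misclassify injection-site or flu-like reactions

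*Combined protocol and SAP*

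**What the plan says.** SAP 3.7.2 introduces its date rules by saying that "the following imputation rules will be applied to impute missing date under conservative principles". For end dates with the year present there are three branches.

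- Month and day missing, and the year is "the same as the year of the last dose of Study Drug then assign the month-day of the last dose of Study Drug".
- Month and day missing, any other year: "otherwise, assign December 31".
- Day only missing: "If only day is missing then assign the last day of the month".

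One conflict rule follows: "If the imputed start date is later than the imputed end date then set the imputed start date to the imputed end date".

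Two safety summaries in the same section depend on AE dates. Criterion A for a local cutaneous reaction at the injection site (LCRIS) covers moderate or severe events with one of four preferred terms "that started on the day of injection, persisted for at least two days or ongoing". Criterion B covers any injection-site AE that is the principal reason for stopping study drug, with no duration test. Flu-like reactions are either (A) influenza like illness, or (B) a fever-type term plus at least two of three named symptoms. The definition closes with the timing "starting on day of injection or the next day".

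AE collection does not stop at the last dose. Protocol 9.4.2 says "The recording of non-serious AEs will begin after the patient signs the ICF and will stop at the end" of follow-up, which is the Post-Treatment Week 15 or early-termination visit. Protocol 6.1.3 places Week 15 at 99 days after the last dose. Protocol 3.4.3 says 14 weeks, which is 98 days; nothing here turns on the one-day difference.

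**The concern.** The first branch ends an event at the last dose although the trial goes on collecting AEs for about 14 weeks afterwards. An AE that began or continued in that period can therefore receive an end date that is too early, sometimes earlier than its onset. The other two branches use the latest date compatible with what was recorded, so this branch is the odd one out.

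Safety and tolerability is a primary objective, and LCRIS and flu-like reactions each have their own incidence table and per-injection percentage. The end date, or a start date dragged back to it, can decide whether an event enters those tables. A record that ends before it begins would also have to be explained in the listings.

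**Working it through.** The plan gives no figure to reproduce. The check applies the start, end and conflict rules as written to example records.

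**Inputs.** Assumed first dose 10 Jan 2022. The last planned dose is on Day 505 (Protocol Appendix A), so the last dose is 10 Jan 2022 + 504 days = 29 May 2023. Week 15 is 99 days later, 5 Sep 2023. In records 1 to 4 the end date is recorded only as 2023.

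| Record | Start | Imputed start | Imputed end | Result |
|---|---|---|---|---|
| 1 | 8 Jul 2023 (known) | none needed | 29 May 2023 | 29 May − 8 Jul = −40 days |
| 2 | Jul 2023, day missing | 1 Jul, then reset to 29 May | 29 May 2023 | Moved onto the last injection day |
| 3 | 29 May 2023, injection-site reaction | none needed | 29 May 2023 | 0 days by difference, 1 day inclusive |
| 4 | May 2023, or 2023 only | 1 May, or 1 Jan | 29 May 2023 | No conflict, no move |
| 5 | Jul 2023, end recorded as 2024 | 1 Jul 2023 | 31 Dec 2024 | Branch not triggered |

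**Record 1.** The conflict rule refers to an imputed start. This start is known, so nothing repairs the negative duration. If the rule were read to cover every start, a known date would be moved back instead. One fault arises on either reading.

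**Record 2.** The recorded month is overridden. The event now satisfies the flu-like timing test. For influenza like illness this matters only if the timing clause covers limb (A). For limb (B) the moved event must also combine with the other required terms.

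**Record 3.** The event fails the two-day test under either way of counting, so it is not an LCRIS under criterion A. An ongoing event has no end date to impute, and one that is the principal reason for discontinuation qualifies under criterion B.

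**What does not change.** SAP 3.7.2 sets treatment-emergent status by comparing the AE start with the first dose. A start moved to the last-dose date does not fall before the first dose, so incidence of treatment-emergent AEs is unaffected.

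**Size of one lost LCRIS.** For a patient with all 20 planned doses (Protocol 6.1.2), the per-injection percentage falls by 1/20 = 5 percentage points. Over 40 patients the mean falls by 5/40 = 0.125 points. LCRIS incidence falls by at most 1/40 = 2.5 points overall.

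**Same records under the proposed rule.** The end date becomes the earlier of 31 Dec and 5 Sep 2023, that is 5 Sep. Record 1 lasts +59 days. Record 2 keeps its July start. Record 3 runs 29 May to 5 Sep, 100 days inclusive, and passes the two-day test. Using 31 December alone would give 176 days for record 1 and 217 days inclusive for record 3, both running past the end of follow-up.

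**The case against.** The strongest reply is that the trigger is rare and the reach short. AEs are assessed at Post-Treatment Weeks 5, 9 and 15 (Protocol Appendix A). Resolution dates must be documented (Protocol 9.4.3.6). Edit checks prompt for missing data, and the database locks only after queries are resolved (SAP 2.5.1). An AE still present when the patient leaves is coded as persisting (Protocol 9.4.3.5). For an AE with onset after the last dose, the site would have to know the year of resolution but not the month, within a window of about 14 weeks. Only a reaction at the last of up to 20 injections can fail the two-day test; one at an earlier injection that year receives the later last-dose date and passes. The flu-like error needs two incomplete dates in one record, and it adds a reaction attributed to the drug. It is therefore not anti-conservative, and the SAP does not define conservative.

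All of this stands as a limit on size. None of it repairs the rule: no other text prevents an imputed end from preceding a known start or protects a recorded start month.

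A reader might infer more than the documents support:

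- That post-treatment AEs in general are misdated. Only year-only end dates in the last-dose year are affected.
- That AE tables or durations are distorted. The other planned AE incidence summaries do not use the end date, and no duration analysis appears in the visible text.
- That about 86% of post-treatment AEs are affected, because about that share of post-treatment days falls in the last-dose year if last-dose dates are spread evenly. That is a share of days under an assumption; it says nothing about how many end dates are incomplete.

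**Conclusion.** The rule is wrong as written, within a narrow scope. It applies when an AE end date is known only to the year and that year is the year of the last dose. It can then put the end before a known start, move a partly known start back onto the last injection day, or remove a last-injection reaction from LCRIS criterion A. The effect is confined to LCRIS, flu-like reactions and listings. The errors run in both directions, since a true LCRIS can be lost and a false flu-like reaction gained.

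The number of such records is not given; it is probably very small and could be zero. One misclassified reaction would be visible in a trial of about 40 patients but would not change its conclusions. The conclusion rests on literal use of the imputation text. Its flu-like part for influenza like illness also depends on reading the timing clause as covering limb (A). This is a minor correction.

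**What to change.** Amend SAP 3.7.2 as follows.

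1. For a year-only end date, in every year, assign the earlier of 31 December of that year and the patient's last date on study (already defined in SAP 3.7.1), but never a date before the AE start.
2. Replace the conflict rule. When an imputed end falls before the start, move the end to the start. Never move a start out of its recorded month or year. Give the recorded part of an end date the same protection: where the start is wholly missing, or known only to the year, and the recorded end precedes the start assigned to it, the start may still be set to the end as now.
3. Classify LCRIS and flu-like reactions from the dates so imputed, so that every event has a defined status, and flag records with imputed dates in the listings.
4. State whether the flu-like timing clause covers limb (A).

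The cost is SAP wording and a small programming change. No new data are needed.

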3.7.3. Vital Signs Measurements

Vital signs will include heart rate, respiratory rate, body temperature, calculated BMI, and systolic and diastolic blood pressure. Vital signs will be summarized for vital sign values as well as the change and percent change from Baseline at each post-baseline visit.

3.7.4. Laboratory Measurements

Bone biomarkers, pituitary axis, thyroid panel, inflammatory, lipid panel, chemistry, hematology, coagulation, cardiac biomarkers and urinalysis (result, change and percent change from Baseline) will be summarized at each post-baseline visit. Listing of laboratory assessments in Chemistry, Hematology and urinalysis will be provided. Local laboratory data will also be provided in the listings separately.

For Alanine Aminotransferase (ALT) and Aspartate Aminotransferase (AST), the number and percent of subjects falling in each of the following categories will be tabulated:

- ALT/AST $> 3 \times \text{ULN}$, confirmed
- ALT/AST $> 5 \times \text{ULN}$, confirmed

For Total Bilirubin (BILI), the number and percent of subjects falling in each of the following categories will be tabulated:

- BILI $> 1 \times \text{ULN}$, confirmed

A confirmed value is based on a consecutive lab value performed on a different day to, but within 7 days of, the initial value. If the repeated value is in the same or worse category, then the initial value is considered confirmed. If the consecutive value is in a better category, then the initial value is confirmed using the consecutive value category. If values that are not confirmed due to failure to retest or missing lab values, then the initial value is presumed confirmed.

If there are multiple results on the same day (no matter from the same lab vendor or different lab vendors), then the worst value will be utilized in the analysis.

The number and percentage of patients falling in each of the following categories (using available central and local laboratory assessments) based on post-baseline assessments will be provided:

- Confirmed Platelet count 100,000/mm³ to lower limit of normal (based on central lab)
- Confirmed Platelet count 75,000 to $< 100,000/\text{mm}^3$
- Confirmed Platelet count 50,000 to $< 75,000/\text{mm}^3$
- Confirmed Platelet count 25,000 to $< 50,000/\text{mm}^3$
- Confirmed Platelet count $< 25,000/\text{mm}^3$
- Confirmed $\geq 30\%$ Platelet count decrease from Baseline; further classifying by the lower limit of normal (Above or below)

Additional analysis to explore the possible thrombocytopenia incidence can also be found in AESI described in Section 3.7.1.

Subjects with more than one confirmed value will be counted exactly once under the worst confirmed category.

3.7.5. 12-Lead Electrocardiograms (ECG)

Safety 12 lead ECG will be performed at the visits indicated in the protocol Schedule of Procedures.

The ECG data will include ventricular rate (VR), PR interval, QRS duration, QT, and corrected QT intervals, and overall interpretation.

For the continuous variables above, descriptive statistics (n, mean, standard error, standard deviation, median, 25th percentile, 75th percentile, minimum and maximum) of the results at each study visit, as well as the change and percent change from Baseline to each study visit, will be presented in summary tables; for the categorical responses to overall interpretation, the results at each visit will be summarized by counts and percentages. In addition, patients reported QT interval > 500 msec and QT interval increase more than 60 msec from Baseline will be summarized at each visit. All the ECG data collected will be listed.

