5.2. Exclusion Criteria

1. Clinically significant (CS) abnormalities in medical history according to Investigator judgement (e.g., previous acute coronary syndrome within 6 months of Screening, major non-pituitary surgery within 2 months of Screening) or from Screening physical examination (PE)
2. Patients who received surgery for pituitary adenoma within the last 3 months before the trial, and/or planning to receive surgery during the trial
3. Patients who received radiotherapy for pituitary adenoma within the last 2 years before the trial, and/or planning to receive radiotherapy during the trial
4. Patients with a pituitary tumor that, per Investigator judgment, is worsening (e.g., either growing, or at risk of compressing or abutting the optic chiasm or other vital structures) as assessed by pituitary/sellar MRI protocol at Screening or within 3 months of Screening. CT scan is allowed if MRI is contraindicated

5. Evidence of decompensated cardiac function per medical judgement and/or New York Heart Association (NYHA) Class 3 or 4
6. Clinical evidence of symptomatic hyperprolactinemia that would necessitate treatment
7. Symptomatic cholelithiasis, and/or choledocholithiasis
8. Intentionally left blank
9. Patients with history of hypoglycemia unawareness (who have had > 3 severe episodes in the past 6 months) or documented reactive hypoglycemia
10. Screening laboratory results as follows, or any other CS abnormalities in Screening laboratory values that would render a patient unsuitable for inclusion (abnormalities may be retested for eligibility purposes)
 - a. UPCR ≥ 500 mg/g. In the event of urine protein/creatinine ratio (UPCR) above this threshold eligibility may be confirmed by a quantitative total urine protein measurement of < 1000 mg/24 hr
 - b. Positive test (including trace) for blood on urinalysis. In the event of a positive test eligibility may be confirmed with urine microscopy showing ≤ 5 red blood cells per high power field
 - c. alanine aminotransferase (ALT) or aspartate aminotransferase (AST) $> 1.5 \times$ ULN; alkaline phosphatase (ALP) $> 3 \times$ ULN; Total bilirubin $\geq 1.5 \times$ ULN. Patients with Gilbert's syndrome may have total bilirubin $\geq 1.5 \times$ ULN if only the indirect bilirubin is elevated $>$ ULN and the ALT/AST is not greater than the ULN.

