 - d. eGFR < 45 mL/min/1.73 m² as determined by the Chronic Kidney Disease-Epidemiological Collaboration (CKD-EPI) equation for creatinine clearance OR serum creatinine > 1.8 mg/dL in males and > 1.5 mg/dL in females
 - e. Platelet count $< 125,000$ mm³
 - f. Abnormal thyroid function tests must be discussed with the Sponsor Medical Monitor or Designee
 - g. HbA1c $> 10\%$
 - h. Abnormal morning cortisol test demonstrating symptomatic adrenal insufficiency based on Investigator judgement
11. Active infection requiring systemic antiviral or antimicrobial therapy that will not be completed prior to Study Day 1
12. Unwillingness to comply with study procedures, including follow-up, as specified by this protocol, or unwillingness to cooperate fully with the Investigator
13. Active infection with human immunodeficiency virus (HIV), hepatitis C (HCV) or hepatitis B (HBV) diagnosed by initial serology testing and confirmed with RNA testing, or prior treatment for HCV. Patients at Screening who test positive by serology, but negative by RNA may be allowed in consultation with the Sponsor Medical Monitor or Designee
14. Malignancy within 5 years, except for basal or squamous cell carcinoma of the skin, carcinoma *in situ* of the cervix, follicular Stage 1 or papillary thyroid cancer that has been successfully treated; patients that have been treated with curative intent and which have

no recurrence within 5 years may also be eligible if approved by the Sponsor Medical Monitor or Designee

15. Treatment with another investigational drug, biological agent, or device within 1 month of Screening, or 5 half-lives of investigational agent, whichever is longer
16. Treatment with any non-ION- or ISIS-oligonucleotide (including small interfering ribonucleic acid [siRNA]) at any time or prior treatment with an ION- or ISIS-oligonucleotide within 9 months of Screening. Patients that have previously received only a single-dose of an ION- or ISIS-oligonucleotide as part of a clinical study may be included as long as duration \geq 4 months has elapsed since dosing. This exclusion does not apply to vaccines (neither mRNA nor viral vector vaccines)
17. History of bleeding diathesis or coagulopathy
18. Recent history of, or current drug or alcohol abuse that could affect study compliance per Investigator judgment

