Alkaline phosphatase increased	>ULN - 2.5 x ULN if baseline normal 2.0 - 2.5 x baseline if baseline abnormal	>2.5 - 5.0 x ULN if baseline normal >2.5 - 5.0 x baseline if baseline abnormal	>5.0 x ULN if baseline normal >5.0 x baseline if baseline was abnormal
Alkalosis	pH >normal, but ≤7.5	-	pH >7.5
Aspartate aminotransferase increased	>ULN - 3.0 x ULN if baseline normal 1.5 - 3.0 x baseline if baseline abnormal	>3.0 - 5.0 x ULN if baseline normal >3.0 - 5.0 x baseline if baseline abnormal	>5.0 x ULN if baseline normal >5.0 x baseline if baseline abnormal
Blood bilirubin increased	>ULN - 1.5 x ULN if baseline normal >1.0 - 1.5 x baseline if baseline abnormal	>1.5 - 3.0 x ULN if baseline normal >1.5 - 3.0 x baseline if baseline abnormal	>3.0 x ULN if baseline normal >3.0 x baseline if baseline abnormal
Cardiac troponin I increased	Levels above the upper limit of normal and below the level of myocardial infarction as defined by the manufacturer	-	Levels consistent with myocardial infarction as defined by the manufacturer

Adverse Event	Mild	Moderate	Severe
Cardiac troponin T increased	Levels above the upper limit of normal and below the level of myocardial infarction as defined by the manufacturer	-	Levels consistent with myocardial infarction as defined by the manufacturer
CD4 lymphocytes decreased	<LLN - 500/mm ³ ; <LLN - 0.5 x 10 ⁹ /L	<500 - 200/mm ³ ; <0.5 - 0.2 x 10 ⁹ /L	<200/mm ³ ; <0.2 x 10 ⁹ /L
CPK increased*	>ULN - <6 ULN	6 - 10 x ULN	>10 x ULN
Creatinine increased**	>ULN - 1.5 x ULN if baseline normal > 1.0 - 1.5 x baseline if baseline abnormal	>1.5 - 3.0 x ULN if baseline normal >1.5 - 3.0 x baseline if baseline abnormal	>3.0 x ULN if baseline normal >3.0 x baseline if baseline abnormal
GGT increased	>ULN - 2.5 x ULN if baseline normal 2.0 - 2.5 x baseline if baseline abnormal	>2.5 - 5.0 x ULN if baseline normal >2.5 - 5.0 x baseline if baseline abnormal	>5.0 x ULN if baseline normal >5.0 x baseline if baseline abnormal
Hypercalcemia	Corrected serum calcium of >ULN - 11.5 mg/dL; >ULN - 2.9 mmol/L; Ionized calcium >ULN - 1.5 mmol/L	Corrected serum calcium of >11.5 - 12.5 mg/dL; >2.9 - 3.1 mmol/L; Ionized calcium >1.5 - 1.6 mmol/L; symptomatic	Corrected serum calcium of >12.5 mg/dL; >3.1 mmol/L; Ionized calcium >1.6 mmol/L; hospitalization indicated

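### SAP 3.7.4 counts total bilirubin above ULN with no baseline condition, although the entry criteria admit patients who are already above ULN

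*Combined protocol and SAP*

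**What the plan says.** **Safety categories (SAP 3.7.4).** The bilirubin table is introduced by "For Total Bilirubin (BILI), the number and percent of subjects falling in each of the following categories will be tabulated" and has one row, "BILI $> 1 \times \text{ULN}$, confirmed". The mildest platelet row is "Confirmed Platelet count 100,000/mm³ to lower limit of normal (based on central lab"). Neither row asks whether the patient was already in the category before the first dose. The platelet list is said to use post-baseline assessments; the bilirubin sentence gives no window. The platelet list also has a row for a confirmed fall of at least 30% from Baseline, split by LLN. Bilirubin has no comparable row.

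**Confirmation (SAP 3.7.4).** A value is confirmed by a further value on another day within 7 days. Otherwise: "If values that are not confirmed due to failure to retest or missing lab values, then the initial value is presumed confirmed".

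**Entry limits (Protocol 5.2).** Criterion 10c excludes "Total bilirubin $\geq 1.5 \times$ ULN", then makes an exception: "Patients with Gilbert's syndrome may have total bilirubin" at or above that limit, provided only indirect bilirubin is raised and ALT/AST do not exceed ULN. Criterion 10e excludes "Platelet count $< 125,000$ mm³".

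**Adverse event grading (Protocol Appendix D).** The mild grade for raised bilirubin is ">ULN - 1.5 x ULN if baseline normal >1.0 - 1.5 x baseline if baseline abnormal", so it is relative to the patient's own baseline when that baseline is abnormal.

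**The concern.** A safety incidence row should separate what appeared or worsened after dosing from what the patient brought into the trial. The bilirubin row cannot do this, because its threshold lies below the entry limit. Safety and tolerability form a primary objective (Protocol 1.1.1) and there is no untreated arm, so the reader has no concurrent background rate against which to judge the count. The label *confirmed* also suggests a check that will often not have been made.

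The rule differs from how the documents treat pre-existing findings elsewhere. Under Protocol 9.4 a pre-existing condition is not an adverse event unless it worsens. Under SAP 3.7.2 a linked pre-dose event becomes treatment-emergent only if its later record is worse.

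**Working it through.** **1. Entry limits against safety categories.**

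| Parameter | Admitted at entry | Lowest SAP 3.7.4 row | Overlap |
|---|---|---|---|
| ALT/AST | up to 1.5 × ULN | > 3 × ULN | none |
| Total bilirubin | below 1.5 × ULN; higher in qualifying Gilbert's patients | > 1 × ULN | > 1.0 to < 1.5 × ULN, and above for Gilbert's |
| Platelets | 125,000/mm³ and above | 100,000/mm³ to LLN | 125,000 to LLN, only if LLN > 125,000 |

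The bilirubin overlap follows from the documents alone. The platelet overlap depends on an LLN that they do not give. Over an assumed LLN range, with share of the category's width = (LLN − 125,000)/(LLN − 100,000):

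| Assumed LLN (/mm³) | Overlap | Share of category width |
|---|---|---|
| 120,000 or 125,000 | none | 0 |
| 130,000 | 125,000–130,000 | 5/30 = 0.17 |
| 140,000 | 125,000–140,000 | 15/40 = 0.38 |
| 150,000 | 125,000–150,000 | 25/50 = 0.50 |

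**2. Does confirmation filter these patients?** A retest of a stable elevation would simply agree with it. In most cases there will be no retest:

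- Protocol 8.5.1 triggers repeat liver tests on ALT or AST, not on bilirubin alone.
- Protocol Table 4 prescribes no action above 100,000/mm³ and monitoring every 2 or 4 weeks.
- Scheduled visits are nominally at least 14 days apart, outside the 7-day window.

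The value is then presumed confirmed. SAP 3.2.1 lets unscheduled results into the abnormality counts and names AST, ALT, platelet and renal tests. Bilirubin is not named, so it is unclear whether an unscheduled bilirubin retest would be used at all.

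**3. Denominator.** The plan's own figure reproduces. SAP 3.3.3 assumes a 27.5% reduction with SD 30%, so d = 27.5/30 = 0.917. The exact two-sided one-sample t-test at 5% has power 0.824 with n = 12 and 0.782 with n = 11. Three groups of 12 with 10% drop-out give 36/(1 − 0.10) = 40 randomized. Safety tables use the Safety Set (all randomized and dosed patients), so about 40 is the relevant total, not 36.

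**4. Size.** One carried-over patient adds 1/40 = 2.5 points overall; four add 4/40 = 10.0 points. The documents give no baseline prevalence of bilirubin above ULN. For an assumed prevalence p, with no drug effect, the expected count is 40p and P(at least one) = 1 − (1 − p)^40:

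| Assumed p | Expected carried-over cases | P(at least one of 40) |
|---|---|---|
| 2% | 0.8 | 55.4% |
| 5% | 2.0 | 87.1% |
| 10% | 4.0 | 98.5% |

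If patients already in the category at baseline are separated out, the carried-over count becomes 0 in each line.

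**The case against.** The best defence is that these are descriptive counts in a small trial that also plans by-visit change and percent change from Baseline, plus chemistry and hematology listings. With about 40 patients, anyone can look up the baseline of each flagged case. Presuming unretested values confirmed matches the liver stopping rules in Protocol 8.6.1 and errs towards over-reporting. All of this is true, and it keeps the point modest. It does not correct the incidence row, which is the number likely to be carried into a summary.

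Several stronger readings are tempting but not supported:

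- *The platelet row is inflated too.* This needs an LLN above 125,000/mm³, which is nowhere stated. Even then, the row for a fall of at least 30% from Baseline leaves out a patient who stays at 130,000/mm³.
- *The SAP contradicts Appendix D.* Appendix D grades adverse events, whereas the SAP row is a threshold count. Appendix D also grades platelets on absolute limits. It is a useful model for bilirubin, not proof of a conflict.
- *Each case adds 1/12 = 8.3 points to a dose group.* Twelve is the evaluable number per treatment group. SAP 3.7 tabulates safety by maximum dose received, and those group sizes are not stated.
- *Almost every stable patient will cross ULN over repeated visits.* With 26 post-baseline visits (23 on treatment, 3 after), assumed independent and lognormal, a patient whose true level is 0.8 × ULN has about a 28%, 84% or 97% chance of at least one value above ULN at an assumed within-patient CV of 10%, 15% or 20%. The answer depends on an undocumented CV. It also concerns chance crossing from a normal baseline, which is a different problem and one that a worsening rule would not remove.

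**Conclusion.** The point holds for bilirubin. Followed exactly, SAP 3.7.4 counts as a finding a patient who entered above ULN, as criterion 10c permits, and did not change. Each such patient adds about 2.5 percentage points overall, on the assumption that about 40 patients are dosed. The number of such patients is unknown; at assumed prevalences of 2% to 10% the expected number is 0.8 to 4.0. For platelets the point is conditional on the central-laboratory LLN and partly offset by the decrease-from-Baseline row.

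A reader might infer that the safety conclusions as a whole are unreliable. The documents do not support that. The ALT/AST rows do not have this problem, baseline-relative summaries and listings are planned, and neither the primary efficacy analysis nor any hypothesis test uses these rows. The change is worth making because it is cheap and safety is a primary objective.

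**What to change.** In SAP 3.7.4:

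1. Count a patient in the bilirubin row, and in the mildest platelet row, only if the worst post-baseline category is worse than the baseline category; or present a baseline-to-worst-post-baseline shift table.
2. For bilirubin the shift table is the better choice. With one category above ULN, a worsening rule alone would hide any further rise in a patient already above ULN, including those with Gilbert's syndrome. Use multiples of ULN, or of baseline where baseline is abnormal; the Appendix D boundaries of 1.5 and 3.0 would serve.
3. State that the bilirubin row uses post-baseline values, and state the central-laboratory platelet LLN.
4. For rows with no prescribed 7-day retest, confirm with the next available value or drop the word *confirmed*. This is a tabulation rule and asks for no additional testing.

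The cost is SAP wording, some programming and slightly more table space; no new data are needed. Some reported incidences will be lower than under the current rule, so the tables should state the rule used.
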